### **Data Collection:**

*Pre-test:* Prior to implementation, the self-screening tool will be pre-tested with 5 older adults attending participating seniors centres/organizations. The purpose of the pretest will be to identify any implementation issues such as recruitment, administration, understanding and ease of use of the self-screening tools.

*Procedures:* Older adults assigned to both groups will receive follow up from the RA who will provide details about the study and answer any questions. Prior to randomization, consenting older adults from both groups will complete a demographic (e.g., age, sex, highest level of education, household income), health history profile (e.g., co-morbidities, history of previous referrals for UI, medications) (**see Demographic and Health History Profile**) and a quality of life questionnaire (**see The King's Health Questionnaire**).

Three months following study entry participants from both groups will receive a phone follow-up to obtain information about actions they have taken re IU (e.g., self/physician

referral), UI symptoms,  treatments received, satisfaction with care (**See Three Month Follow up Questionnaire**), and changes in quality of life. The follow up phone call will be recorded. It is expected the baseline and 3 month follow up data collection will take approximately 20-30 minutes to complete.

The primary outcome will be the numbers of older adults who take action to receive help for their UI during the 3-month follow-up from study entry: self-referral to the local UI clinic, appointment with GP about their UI, and/or referral to a specialist (urologist or urogynecologist or gynecologist), or other action. Secondary outcomes will include: treatments received, satisfaction with care, changes in quality of life.

**Post-Intervention Focus Groups:** To obtain feedback on the self-screening process, focus groups (n=2) will be conducted with older adults (10-12 participants) who were in the self-screening group. At the end of 3-months from study entry, in conjunction with survey completion, participants will be invited to participate in a focus group. Those expressing an interest in focus group participation will be contacted with details of the date, time of the focus group and will receive a copy of the semi-structured interview questions. Questions will address participants' comfort with the self-screening process, rationale and influences on choice to self-refer or not, barriers/facilitators to self-referral, recommendations to make the self-screening process easier (**See Focus Group Interview Questions**).

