Health Planning Society, Westside Health Network, Seniors Outreach Bureau) serve large and different populations of seniors (>300 seniors) so overlap in membership is not expected to be an issue.

**Sampling and Recruitment:** The study sample will include older adults  $\geq 65$  years of age (men and women) who attend a local Senior's Centre or organization, report having some UI symptoms, are independent living, ambulatory, with no more than mild cognitive impairment, able to read and write in English or have someone who can assist with reading the data collection information and can complete a paper survey independently. Older adults will be excluded if they have cognitive impairment, require more than minimal assistance with completing the survey, or have any impairment (e.g., vision) that would make self-screening and follow up challenging. They must also never have been referred to a UI specialist or program in the past.

Following ethics approval, eligible older adults will be recruited through a letter of invitation sent through e-mail distribution lists of our participating seniors centres/organizations (**see Letter of Invitation**). Based on other UI studies, in which there was a 14% self-referral rate without an intervention, we hypothesize a 61% incremental increase in self-referral in the arm receiving the intervention. The sample size required to detect an improvement in self-referral (with 80% power,  $p < .05$ ) to a health professional (e.g., UI specialist) is 24 participants (12 older adults per arm). Drop-out or attrition is common in research studies. In factoring the potential for a drop-out rate of 50%, a sample size of 36 participants will be recruited. Excel randomization function will be used to assign participants to one of the two arms (the arm receiving the self-screening process or the arm not receiving this process). The randomization assignments (allocations) will be placed in individual sealed envelopes. After informed consent is obtained, the Research Assistant (RA) will choose the next available envelope to reveal which arm the study participant will be assigned.

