#### *Primary analysis:*

The study hypothesis is that older adults exposed to the self-screening process will follow-up with health professionals to receive help for their UI condition more often than the control group. To test this hypothesis, investigators will calculate the proportion (with 95% CI) of participants who self-report as having self-referred to a health professional (binary yes/no response) during the study period for each group. A chi-square test will be conducted to determine if the self-screening process is associated with self-referral to a health professional. In addition, a logistic regression analysis will be conducted to model the odds of self-referring among people who have undergone self-screening, adjusting for demographics, and health history variables. Bivariate analysis will be conducted and variables significantly associated with self-referral will be entered into the model. Since the study sample size will only allow for having 3 variables in the

model, more than one regression model may be necessary. If this is the case, a Bonferroni adjustment will be used to account for multiple comparisons.

*Secondary analysis:*

Quality of life scores will be compared within and between groups. For the within group comparison a two-sided dependent t-test will be conducted using the pre-study and 3-month quality of life scores for each group. To determine if a change in quality of life (difference between pre-study and 3-month quality of life scores) is statistically significant and mixed between-within subjects analysis of variance will be conducted.

All participants will complete a Urinary Symptoms questionnaire (ICIQ-FLUTS) which consists of ordinal categorical responses to questions related to urinary symptoms. Each question has five response options. For each question, each response category will be assigned a numeric value depending on the severity of the symptom (1= no symptoms; 5=severe symptoms). For each participant, improvement in symptoms will be determined by a reduction in the ordinal value. Improvement in UI symptoms will be compared between groups using a chi-square test.

Investigators are also interested in knowing if self-screening results in a higher proportion of participants initiating medication of UI during the study period. Therefore, the proportion of participants in each group who started medication for UI during the study period will be compared using a chi-square test.

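### No masking of the 3-month outcome assessment is described, and a focus-group invitation for the self-screening arm only is tied to the contact that collects the self-reported primary outcome

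*Combined protocol and SAP*

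**What the plan says.** Under Data Collection (Procedures), the outcome contact is a telephone call in both arms: "Three months following study entry participants from both groups will receive a phone follow-up to obtain information about actions they have taken re IU". The same section adds: "The follow up phone call will be recorded". The primary outcome defined there counts self-referral to the local clinic, a GP appointment about incontinence, "and/or referral to a specialist (urologist or urogynecologist or gynecologist), or other action". The Primary analysis section reduces this to the proportion of "participants who self-report as having self-referred to a health professional (binary yes/no response"), compared by chi-square.

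Under Post-Intervention Focus Groups, the groups are for "older adults (10-12 participants) who were in the self-screening group". The invitation is issued at 3 months: "in conjunction with survey completion, participants will be invited to participate in a focus group".

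The only staff role named as dealing with participants is the Research Assistant. Under Sampling and Recruitment, after consent, "the Research Assistant (RA) will choose the next available envelope to reveal which arm the study participant will be assigned". Under Procedures, "Older adults assigned to both groups will receive follow up from the RA who will provide details about the study".

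The combined protocol and SAP does not mention masking of the caller, the coder or the analyst. It does not say who makes the 3-month call, who issues the invitation, or whether the invitation comes before or after the outcome questions.

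**The concern.** One arm completes a symptom questionnaire and receives a fact sheet and clinic contact details; the other gets neither. Participants therefore cannot be blinded, and masked collection or coding is the main safeguard still available. The plan does not provide it, and two features make it likely that the arm is known when the outcome is recorded. An invitation restricted to one arm is attached to the outcome contact, and the one named staff role in contact with participants sees the allocation.

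Judgement can enter in two places: how far a vague answer is probed, and whether it is scored 'yes'. The open category in the outcome definition leaves room for both. So does the difference in wording between Procedures (any listed action) and Primary analysis (self-referral), which is a separate issue in itself. Someone who knows the arm could, without intending to, probe harder or score more generously in the self-screening arm. That would push the result towards the hypothesis. The Limitations section considers only a bias towards the null.

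**Working it through.** **1. Does the plan make the arm known to the assessor?** Setting the sections side by side:

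- Procedures: the 3-month call collects the outcome in both arms; the caller is not named.
- Post-Intervention Focus Groups: the invitation goes with survey completion at 3 months and is for one arm. Whoever issues it must know the arm.
- Sampling and Recruitment: the Research Assistant learns the arm from the envelope.

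That survey completion and the telephone call are one contact handled by one person is a reasonable inference, not a statement in the plan. The supportable conclusion is that the arm may well be known, and that nothing in the plan prevents it.

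**2. The plan's own figure.** Inputs from Sampling and Recruitment: control rate 14%; 61% incremental increase, read as percentage points, giving 75%; 80% power; 0.05, taken as two-sided; 12 per arm.

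- Mean rate: (0.14 + 0.75)/2 = 0.445.
- n = [1.96·√(2·0.445·0.555) + 0.842·√(0.14·0.86 + 0.75·0.25)]² / 0.61² = 9.14, so 10 per arm.
- With continuity correction: (n/4)·[1 + √(1 + 4/(n·0.61))]² = 12.2, so 13 per arm, or 26 in total.

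The stated 24 is within 2 participants of that. Exact power at 12 per arm is 0.832 with Fisher's test and 0.924 with uncorrected chi-square. The sample size is not in dispute here; 12 per arm is used below.

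**3. What differential scoring could do.** Assume no true effect and 14% in both arms. Let a share m of true 'no' answers be scored 'yes' in the self-screening arm only. The recorded intervention rate is 0.14 + 0.86·m:

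- m = 10%: 0.226
- m = 20%: 0.312
- m = 30%: 0.398

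At 12 per arm the expected number of true 'no' answers is 0.86 × 12 = 10.3, so m = 10%, 20% and 30% mean about 1, 2 and 3 re-scored people.

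The false-positive rate is the sum, over all pairs of counts (a, b) with p < 0.05, of Bin(a; n, recorded rate) × Bin(b; n, 0.14):

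| m | chi-square, 12 per arm | Fisher, 12 per arm | chi-square, 18 per arm | Fisher, 18 per arm |
|---|---|---|---|---|
| 0 | 2.7% | 0.6% | 4.5% | 1.6% |
| 10% | 6.3% | 2.2% | 9.6% | 4.8% |
| 20% | 15.0% | 7.0% | 22.4% | 13.7% |
| 30% | 28.6% | 15.9% | 41.5% | 28.9% |

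Chi-square here is uncorrected; the plan does not say whether a correction applies. At 12 per arm the Yates-corrected test gives the same figures as Fisher's. The 18 per arm columns are for all 36 recruits retained and split equally.

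**4. Sensitivity to a single answer, 12 per arm.**

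- Uncorrected chi-square: 6 v 2 gives p = 0.083; 7 v 2 gives p = 0.035.
- Fisher: 7 v 2 gives p = 0.089; 8 v 2 gives p = 0.036; 9 v 2 gives p = 0.012.

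Near the threshold one answer decides significance. At about the planned effect (9 v 2), removing one intervention 'yes' does not.

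**The case against.** A reader might infer that the caller is bound to know the arm while scoring. The documents do not support that. The link between invitation and survey is loose enough to allow an invitation after the last outcome question, from another person, or by letter. Nor do they say that the Research Assistant makes the call or codes the answers. A reader might also infer that the invitation destroys masking that would otherwise exist, but no masking is described to begin with. If the Research Assistant does call, the arm is already known from the envelope, and moving the invitation alone would not change that. This stands, and it is why the fix needs arm-hidden coding as well.

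Calling the outcome subjective would go too far. Whether someone saw a GP or contacted a clinic is a factual self-report; judgement enters mainly through the open category and through vague answers. It would also be too strong to say that the bias could never be detected. The recording lets a masked rater check the coding later, although it cannot undo unequal probing.

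The 3-month questionnaire is cited but is not among the documents reviewed, and it may already put fixed help-seeking questions first. The miscoding shares have no source in the documents, and the inflation is markedly smaller with Fisher's test.

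Finally, participants know their arm, so their own reporting may differ under any caller, and some will reveal it. That is true, but the staff-side part is the part the sponsor can control. Pilot status does not remove the point either, because the plan sets out to test effectiveness and specifies a hypothesis test.

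**Conclusion.** The point holds as a gap in the plan, not as proof of biased assessment. No masking of the 3-month assessment is described, and an arm-restricted invitation is linked to the contact that collects the primary outcome. The person recording or coding that outcome may therefore know the arm.

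If differential scoring occurred, its effect would depend on its extent and on the test. At 12 per arm with no true effect, a 20% share gives a false-positive rate of 15.0% with uncorrected chi-square and 7.0% with Fisher's test; at 10%, Fisher's stays at 2.2%. These figures rest on the 14% control rate, on the assumed shares, and on misclassification in one direction and one arm only. They illustrate possible size and do not predict it. The change is worth making because it is cheap and nothing else in the plan covers the risk.

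**What to change.** 1. Ask the help-seeking questions first, from one script identical in both arms, and write the answers down verbatim.
2. Close the outcome form before any focus-group invitation, and send that invitation separately, by letter or e-mail.
3. Have an existing team member who did not handle that participant's allocation code yes/no from the written answer with the arm hidden. Use the recording already planned to settle doubtful answers.
4. State in the plan who makes the 3-month call, and add participants' own reporting bias to the Limitations.

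Cost: a reordered script, a separate invitation, and a few minutes of coding for each of at most 36 people, with no new staff. The downside is that focus-group uptake may be slightly lower than with an invitation made during the call.

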### **Data Analysis:**

#### *Description of Sample:*

Frequency analysis will be conducted on all demographic (age, sex, highest level of education, household income), health history profile (co-morbidities, history of previous referrals for UI, medications) and quality of life. For continuous variables, means with associated standard deviations (SD) will be calculated for parametric variables or medians with associated interquartile ranges will be calculated for nonparametric variables. For categorical variables, percentages with 95% confidence interval (CI) will be calculated. These calculations will be calculated for the total study population as well as for participants in each study group.

#### *Primary analysis:*

The study hypothesis is that older adults exposed to the self-screening process will follow-up with health professionals to receive help for their UI condition more often than the control group. To test this hypothesis, investigators will calculate the proportion (with 95% CI) of participants who self-report as having self-referred to a health professional (binary yes/no response) during the study period for each group. A chi-square test will be conducted to determine if the self-screening process is associated with self-referral to a health professional. In addition, a logistic regression analysis will be conducted to model the odds of self-referring among people who have undergone self-screening, adjusting for demographics, and health history variables. Bivariate analysis will be conducted and variables significantly associated with self-referral will be entered into the model. Since the study sample size will only allow for having 3 variables in the

model, more than one regression model may be necessary. If this is the case, a Bonferroni adjustment will be used to account for multiple comparisons.

*Secondary analysis:*

Quality of life scores will be compared within and between groups. For the within group comparison a two-sided dependent t-test will be conducted using the pre-study and 3-month quality of life scores for each group. To determine if a change in quality of life (difference between pre-study and 3-month quality of life scores) is statistically significant and mixed between-within subjects analysis of variance will be conducted.

All participants will complete a Urinary Symptoms questionnaire (ICIQ-FLUTS) which consists of ordinal categorical responses to questions related to urinary symptoms. Each question has five response options. For each question, each response category will be assigned a numeric value depending on the severity of the symptom (1= no symptoms; 5=severe symptoms). For each participant, improvement in symptoms will be determined by a reduction in the ordinal value. Improvement in UI symptoms will be compared between groups using a chi-square test.

Investigators are also interested in knowing if self-screening results in a higher proportion of participants initiating medication of UI during the study period. Therefore, the proportion of participants in each group who started medication for UI during the study period will be compared using a chi-square test.

**Limitations:** It is possible that screening for eligibility for the study may make a person more likely to self-refer. If this occurs in the control arm, it may bias the results toward the null hypothesis (i.e. it may be less likely to detect a difference between study arms).

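### The declared primary outcome (any action to get help for UI) has no planned test; the primary analysis and sample size use self-referral only

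*Combined protocol and SAP*

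**What the plan says.** Three parts of the combined protocol and SAP bear on this.

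- **Data Collection, Procedures.** "The primary outcome will be the numbers of older adults who take action to receive help for their UI" within three months of study entry. The routes listed are self-referral to the local UI clinic, then "appointment with GP about their UI, and/or referral to a specialist (urologist or urogynecologist or gynecologist), or other action". The same section says the follow-up call will "obtain information about actions they have taken re IU (e.g., self/physician", the next word being referral, so self-referral and physician referral are named as different things. It then adds "Secondary outcomes will include: treatments received, satisfaction with care, changes in quality of life". Self-referral on its own is in neither list.
- **Data Analysis, Primary analysis.** The proportion to be estimated is of "participants who self-report as having self-referred to a health professional (binary yes/no response) during the study period for each group". The hypothesis test is set on that same variable: "A chi-square test will be conducted to determine if the self-screening process is associated with self-referral to a health professional". The logistic regression models the odds of self-referring, and its covariates are chosen by their association with self-referral.
- **Methods, Sampling and Recruitment.** The control rate comes from earlier work "in which there was a 14% self-referral rate without an intervention", to which a 61% incremental increase is added. The size needed to detect improved self-referral "to a health professional (e.g., UI specialist) is 24 participants (12 older adults per arm").

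The Secondary analysis covers quality of life, urinary symptoms and starting UI medication. It does not include the any-action outcome.

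**The concern.** The declared primary outcome and the variable tested under the heading Primary analysis are not the same. A control participant whose physician raises UI and refers them to a urologist is a success under Data Collection and can be a failure under Primary analysis. Control participants receive standard care from their own physicians, so such routes are open to them.

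Three things follow. The declared outcome has no planned between-group comparison. The tested outcome is not a declared one. The 80% power statement applies only to self-referral. With about 12 participants per arm, a handful classified differently can change the conclusion, and the text as it stands would let the choice between definitions be made after the data are seen.

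**Working it through.** **1. The definitions side by side**

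| Route to help | Counts in Data Collection (primary outcome) | Counts in Primary analysis and sample size |
|---|---|---|
| Self-referral to the UI clinic | Yes | Yes |
| GP appointment booked by the participant | Yes, listed separately | Unclear |
| Specialist referral raised by the physician | Yes | No |
| Other action | Yes | No |

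**2. The plan's own sample size, to see which variable it rests on**

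Inputs from Sampling and Recruitment: control 14%; a 61% increase, read as points, so 14% + 61% = 75%; 80% power; 5% significance (taken as two-sided, since the plan does not say); equal arms.

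n per arm = [1.96·√(2p̄(1−p̄)) + 0.842·√(p₁(1−p₁) + p₂(1−p₂))]² / (p₂−p₁)², with p̄ = (0.14 + 0.75)/2 = 0.445.

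- Numerator: [1.96·√0.494 + 0.842·√0.308]² ≈ 3.40. Denominator: 0.61² = 0.372. The ratio is 9.1, so 10 per arm, or 13 per arm with continuity correction.
- Exact power of Fisher's test is 75.9% at 11 per arm and 83.2% at 12 per arm.

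The stated 12 per arm is therefore reproduced for self-referral at 14% against 75%. A relative reading of the 61% (14% against 22.5%) would need 321 per arm, so the points reading is the one that fits.

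**3. Power for the declared composite at 12 per arm**

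Power = Σₐ Σ_b Bin(a; 12, p_C)·Bin(b; 12, p_I)·1{p-value < 0.05}, summed over all 13 × 13 tables. The test is two-sided Pearson (uncorrected) or Fisher. Only the first row uses the plan's rates; the documents give no composite rate, so the other rows are assumptions.

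| Control | Intervention | Pearson | Fisher |
|---|---|---|---|
| 14% (plan, self-referral) | 75% | 92% | 83% |
| 20% | 85% | 96% | 89% |
| 30% | 75% | 67% | 50% |
| 30% | 90% | 92% | 83% |
| 40% | 75% | 46% | 29% |
| 40% | 90% | 79% | 64% |

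A second set of assumptions lets the same share s of non-self-referrers act by another route in both arms: control = 0.14 + 0.86s, intervention = 0.75 + 0.25s.

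| Control | Intervention | Pearson | Fisher |
|---|---|---|---|
| 30% | 79.7% | 76% | 60% |
| 40% | 82.6% | 63% | 45% |
| 50% | 85.5% | 48% | 31% |

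**4. How few participants change the result**

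Hypothetical counts, intervention against control. Pearson χ² = 24(ad − bc)² / (12·12·total yes·total no).

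- Self-referral 9/12 against 2/12: χ² = 24·84²/(144·11·13) = 8.22, p = 0.004 (Fisher 0.012). If three controls act by another route, the composite is 9/12 against 5/12: χ² = 24·48²/(144·14·10) = 2.74, p = 0.098 (Fisher 0.214).
- Self-referral 7/12 against 3/12: p = 0.098 (Fisher 0.214). If three intervention participants and one control act by another route, the composite is 10/12 against 4/12: χ² = 24·72²/(144·14·10) = 6.17, p = 0.013 (Fisher 0.036).

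**The case against.** The best defence is that the analysed variable is loose shorthand for seeking professional help. It refers to health professionals in general, gives a UI specialist only as an example, and is introduced as the test of a hypothesis about following up with health professionals. If a GP visit booked by the participant counts as self-referral, anyone referred onward from that visit is already a yes. What remains is small: referrals after a visit where the participant did not raise UI, and other actions. The Control Group text says most physicians do not ask about UI. The three-month questionnaire, which is cited but not reproduced, might also define the item. Finally, this is a pilot, the composite rates are assumptions, and the example tables were picked to cross 0.05.

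Some of this stands. The broad reading narrows the gap, the power figures show no direction, and the example counts show what is possible rather than likely. It does not close the gap. Data Collection lists the GP appointment apart from self-referral and names self and physician referral as different actions. Even on the broad reading, a referral the physician raised and any other action count in one place and not in the other. Pilot status does not help either, because the Study Design sets out to test effectiveness and the plan makes a power claim and a significance test.

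**Conclusion.** The concern holds. The declared primary outcome is not analysed anywhere, and the primary test and the sample size both belong to a narrower variable that is not a declared outcome. The sample size is not itself wrong on this account: 12 per arm gives 83% exact Fisher power for self-referral at 14% against 75%. For the composite, power is unknown. Under the assumed rates shown it ranges from 96% to 46% (Pearson) and from 89% to 29% (Fisher), so it could fall on either side of 80%. These figures assume 12 evaluable participants per arm, a two-sided 5% test and the percentage-point reading of the increase. The mismatch itself depends on none of them. Because the trial's main conclusion can turn on which definition is used, this must be settled before analysis.

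**What to change.** Make the three sections refer to one variable.

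**Preferred, because it matches the existing test and sample size.**

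- In Data Collection, define the primary outcome as self-referral to a health professional about UI within three months of study entry (yes/no).
- State that it includes self-referral to the local UI clinic, and state whether it includes a GP appointment about UI that the participant booked. If it does, Sampling and Recruitment should say whether the 14% still applies, since the Background describes its source (reference 11) in terms of self-referral to urogynecology.
- Name the any-action composite as a secondary outcome with its own between-group comparison (difference in proportions with 95% CI), and report the other-action category separately and descriptively.

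**Alternative, if the sponsor wants a composite as primary.** The Primary analysis must then test that composite. The open-ended other-action category should be left out of it. Sampling and Recruitment must state assumed composite rates for both arms and restate the power at the planned size.

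**Cost.** Wording in Data Collection and Primary analysis, plus one comparison. The three-month call already asks what actions were taken. Under the preferred option the sample size is unchanged as long as the 14% and 75% still apply; if GP visits are counted, those rates need a fresh justification.
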